**Study Protocol and Analytic Plan for the Individualized Response to Vitamin D Treatment
Study (INVITe)**

NCT02925195

Study Protocol	2
Analytic Plan	18

**Multi-Ethnic Study of Atherosclerosis
Individual Response to Vitamin D Treatment
(MESA-INVITe)**

Study Protocol

Version date: February 2, 2018

GENERAL INFORMATION

Funding Agencies

The National Heart, Lung, and Blood Institute

Program Officers

[name], MHS

MESA Project Officer

Division of Cardiovascular Sciences

National Heart, Lung, and Blood Institute

[name]

[name]

[contact]

[contact]

E-mail: [contact]

Grant Numbers

NIH R01 HL096875 ([name], [name], MPI)

Principal Investigators

[name], MS

Professor

Department of Medicine / Division of Nephrology

University of Washington Kidney Research Institute

[name]

[name]

[name]

[contact]

[contact]

[contact]

[name], MD MS

Associate Professor

Department of Medicine / Division of Nephrology

University of Washington Kidney Research Institute

[name]

[name]

[name]

[contact]

[contact]

[contact]

PROTOCOL SUMMARY

Study Title	Individual response to vitamin D treatment (INVITe)
Objectives	To determine individual genetic and metabolic characteristics that modify the response to cholecalciferol treatment
Study Design	Double blind randomized clinical trial of 16 weeks duration
Participating Centers	University of Washington, Seattle, WA (Coordinating center) Wake Forest University, Winston-Salem, NC (Field center) Columbia University, New York, NY (Field center) Northwestern University, Evanston, IL (Field center) Johns Hopkins University, Baltimore, MD (Field center)
Study Population	1,600 participants from the Multi-Ethnic Study of Atherosclerosis (MESA) study will be recruited from up to 3 different MESA cohorts: 
1. MESA Classic who are returning for their scheduled 6th MESA study visit.2. MESA Air Family and New Recruit participants3. Non-MESA Air Family participants Participants will be recruited from five field centers: Wake Forest University, Winston-Salem, NC; Columbia University, New York, NY; Northwestern University, Evanston, IL; University of California Los Angeles, Los Angeles, CA; and Johns Hopkins University, Baltimore, MD.
	Exclusion criteria 
1. Current use of >1,000 international units (IU) of cholecalciferol daily2. Current use of any activated vitamin D product (calcitriol, paricalcitol, hectorol)3. Known history of allergy or adverse reaction to vitamin D treatment4. Known clinical history of primary hyperparathyroidism5. Known clinical history of kidney stones within the previous 5 years6. Known clinical history of kidney dialysis or transplant.7. Known clinical history of sarcoidosis8. Self-reported history of having elevated serum calcium levels9. Serum calcium level >11 mg/dl at MESA Exam 1 (2000-2002)10. Current participation in another interventional study11. Inability to provide written informed consent
Study Duration	16 weeks
Treatment, Dosage, and Route of Administration	2,000 IU cholecalciferol or inactive placebo taken by mouth once daily
Efficacy Assessments	Change in serum 1,25-dihydroxyvitamin D concentration, serum parathyroid hormone concentration, and blood pressure from baseline to 16-week follow-up visit.

Safety Assessment	Change in urine and serum concentrations of calcium and phosphate from baseline to 16-week follow-up visit. Research staff will assess adverse effects during the study duration by participant self-report.
Modifying Characteristics	The following characteristics will be evaluated for their influence on the biological response to cholecalciferol treatment: genetic polymorphisms, serum concentrations of vitamin D metabolic markers, race, gender, and body mass index.
Statistical Methods	Linear models will be constructed for the follow-up value of each outcome variable. Models will include the initial value of the outcome variable, treatment assignment, and the interaction of treatment with the potential modifying variables.
Date of protocol	February 5, 2018

ABBREVIATIONS

MESA = Multi Ethnic Study of Atherosclerosis

1,25(OH)₂D = 1,25-dihydroxyvitamin D, the activated form of the hormone

25(OH)D = 25-hydroxyvitamin D, the accepted marker of vitamin D storage

Vitamin D₃ = cholecalciferol, the active treatment in the study

PTH = parathyroid hormone

IU = international units

UV = ultraviolet

AE = Adverse event

SAE = Serious adverse event

GFR = glomerular filtration rate

CHSCC = Collaborative Health Studies Coordinating Center

NORC = Nutrition and Obesity Research Center

1. INTRODUCTION

Vitamin D is a vital metabolic hormone that may reduce the risks of cardiovascular diseases, cancer, fractures and other chronic health conditions. Traditionally understood as a calcium regulatory hormone, 1,25-dihydroxyvitamin D (1,25(OH)₂D, the potent hormonal form of vitamin D, binds to its target receptor to regulate the transcription of hundreds of genes relevant to health and disease. Vitamin D receptors are present in nearly all nucleated cells in the body, including those in cardiac muscle and the blood vessel wall. In experimental models, 1,25(OH)₂D promotes endothelial vasodilation, inhibits osteogenic differentiation of vascular smooth muscle cells, prevents cholesterol uptake in macrophages, reduces the progression of ventricular hypertrophy, and suppress the renin-angiotensin system. Cardioprotective actions of vitamin D are further supported by associations of low serum vitamin D concentrations with

hypertension, myocardial infarction, stroke, left ventricular hypertrophy, cancer, and mortality. Large clinical trials are currently testing whether vitamin D treatment will reduce the risks of cardiovascular disease, cancer, and other major health outcomes in the general population.

Published studies demonstrate substantial differences in the individual response to vitamin D treatment. Person-level differences in vitamin D treatment response may be caused by polymorphisms in vitamin D metabolism genes,

variation in race/ethnicity, and/or heterogeneity in functional vitamin D status. Vitamin D₃ (cholecalciferol) is generated in the skin upon exposure to UV light, consumed in the diet, or taken as supplements. Vitamin D₃ is then converted to 1,25(OH)₂D through a series of regulated steps that include transportation, metabolism, receptor binding, and catabolism. These processes are carried out by polymorphic proteins and enzymes that are subject to genetic variation and are closely regulated by internal vitamin D status. Differences in vitamin D metabolism by race and ethnicity have long been suspected due to differences in skin pigmentation. Cutaneous vitamin D₃ synthesis is lowest in African Americans compared to Caucasians; however, 1,25(OH)₂D concentrations are actually higher in African Americans, suggesting more efficient vitamin D utilization or slower vitamin D catabolism.

The goal of this clinical trial is to determine individual-level genetic and metabolic characteristics that modify the response to cholecalciferol treatment. The trial will identify and recruit eligible participants from within the Multi-Ethnic Study of Atherosclerosis (MESA), an ongoing observational cohort study of cardiovascular disease. Results of

this trial will identify novel genetic and biomarker characteristics that influence the vitamin D treatment response in humans and inform relevant subgroup analyses for ongoing vitamin D trials. The use of quantitative vitamin D response variables, comprehensive genotyping of common and rare genetic variants, and novel biomarkers of functional vitamin D status fill important gaps of ongoing trials and will enhance the knowledge to be gained.

2. STUDY OBJECTIVES

This primary aim of this study is to identify genetic polymorphisms, clinical characteristics, and biomarkers that modify the biologic response to vitamin D₃ treatment, assessed by changes in

[figure not shown]

Figure 1. Mechanisms through which vitamin D treatment may prevent selected chronic health conditions. VSMC = vascular smooth muscle cells.

serum concentrations of parathyroid hormone (PTH) and 1,25(OH)₂D and urine calcium excretion.

This secondary aims of this study are to develop improved biomarkers of vitamin D sufficiency based on the individualized response to vitamin D₃ treatment and to create a comprehensive model of vitamin D treatment response based on genetic, clinical, and biomarker characteristics.

3. STUDY DESIGN

This study is double blind, parallel design, randomized clinical trial that will compare treatment with 2,000 international units of cholecalciferol daily by mouth *versus* inactive placebo. Eligible participants will be randomly assigned to receive cholecalciferol treatment or placebo in a 3:1 ratio for a total duration of 16-weeks. The planned sample size is 1,600. Study outcomes are changes in serum concentrations 1,25-dihydroxyvitamin D and parathyroid hormone after 16-weeks. Study procedures will take place at five existing MESA field centers.

4. PARTICIPANTS

We will conduct this vitamin D intervention study within MESA, an ethnically diverse, community-based cohort study. Up to three MESA cohorts will be approached for study recruitment. MESA originally recruited 6,814 participants in 2000-2002 from six U.S. communities: Forsyth County, NC; Northern Manhattan and the Bronx, NY; Baltimore City and [name]; St. Paul, MN; Chicago, IL; and Los Angeles County, CA. MESA Family participants are mainly siblings and parents of MESA Classic participants who were recruited in 2004-2006 for genetics-based studies. MESA Air New Recruit participants were recruited in 2006-2007 from three areas in Rockland County, NY; Riverside County, CA; and Coastal Los Angeles, CA. MESA oversampled by race/ethnicity to create a cohort that was approximately 40% White/Caucasian, 30% Black/African-American, 20% Spanish/Hispanic/Latino, and 10% Asian, primarily Chinese. All MESA Classic and Air New Recruit participants were free of clinical cardiovascular disease at the start of the study. Follow-up MESA examinations occurred 1.5, 3, 5, and 10 years after the baseline exam. A 15-year follow-up study visit (“MESA exam 6”) is ongoing and serves as the source population for this vitamin D trial.

We will recruit a total of 1,600 MESA study participants from five MESA field centers: Wake Forest University, Winston-Salem, NC; Columbia University, New York, NY; Northwestern University, Evanston, IL; University of California Los Angeles, Los Angeles, CA; and Johns Hopkins University, Baltimore, MD. MESA Classic Participants will be recruited at the time of their 6th MESA study examination, scheduled from September 2016 - March 2018. MESA Air and MESA Family participants will be recruited either during follow-up phone calls, or during a MESA INVITE-specific recruitment phone call. Inclusion criteria are active participation in MESA at one of the five field centers and willingness to participate in a clinical trial.

Exclusion criteria

1. Current use of >1,000 international units (IU) of cholecalciferol daily
2. Current use of any activated vitamin D product (calcitriol, paricalcitol, hectorol)
3. Known history of allergy or adverse reaction to vitamin D treatment
4. Known clinical history of primary hyperparathyroidism
5. Known clinical history of kidney stones within the previous 5 years
6. Current or previous history of maintenance kidney dialysis or kidney transplantation

7. Known clinical history of sarcoidosis
8. Self-reported history of having elevated serum calcium levels
9. Serum calcium level >11 mg/dl at MESA Exam 1 (2000-2002)
10. Current participation in another interventional study
11. Inability to provide written informed consent

Standard over the counter vitamin D supplements and multivitamins typically contain between 400-800 IU of vitamin D₃ and *will be allowed* during this trial. If participants are taking >1000 IU of vitamin D daily but would like to participate in INVITe, they may participate if they reduce their total vitamin D supplement dose (from all vitamin D-containing supplements combined) to 1000 IU or less for at least 12 weeks prior to enrollment. Study staff will request that interested participants ask their health care provider whether it is safe for them to temporarily reduce their vitamin D supplement(s). Participants who temporarily reduce their vitamin D supplement(s) will wait at least 12 weeks from their last higher than 1000 IU vitamin D supplement dose prior to completing their baseline INVITe study visit. They can continue to take a total vitamin D supplement dose of up to 1000 IU daily (including 1000 IU daily) during both the 12-week temporary reduction and the 16-week study drug periods.

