8. STUDY PROCEDURES

8.1. *MESA Exam 6.* For MESA Classic participants, baseline data and biosamples for this clinical trial will be obtained from existing procedures that are performed at MESA Exam 6. MESA-INVITe will use some of the MESA Exam 6 baseline data and biosamples, in accordance with the scientific aims and informed consent of the overall MESA study. Types of data that are collected as part of MESA exam 6 that may be used for MESA-INVITe include:

- Demographic information
- Medical and surgery histories
- Social habits (smoking and alcohol use)
- Prescription and non-prescription medication use
- Anthropomorphic measurements (height and weight)
- Blood pressure measurements
- Blood and urine collection

- DNA and RNA collection for epigenomic and transcriptomic analysis

Site investigators at each included MESA field center are co-investigators on this trial. The MESA exam 6 study visits are scheduled from September 2016 - March 2018. Study personnel will mail materials explaining the goals and procedures of this trial to MESA participants and will call participants prior to their Exam 6 visit to review eligibility. At the time of Exam 6, or soon after Exam 6, study personnel will approach potentially eligible subjects, confirm eligibility criteria, explain the details of the trial, and answer relevant questions. The MESA coordinating center will match all medications and supplements reported in the inventory to a known list of vitamin D containing medications in real time to determine the amount of current vitamin D use. For participants who are found to be suitable and interested in this study, MESA personnel will obtain informed consent, consult the MESA Coordinating Center for randomization, and distribute the study medication.

Participants who are unable to use their regularly scheduled Exam 6 as the baseline visit for MESA-INVITe (for example because study staff were unable to start MESA-INVITe at the scheduled Exam 6, or the participant elected to reduce their current vitamin D supplement use [Section 4]) may complete a separate “Exam 6-plus” to collect baseline MESA-INVITe measurements and dispense study medication. All MESA Family and Air participants will use Exam 6-plus visits for basement measurements. In these cases, “Exam 6-plus” will include informed consent, a medical history focused on MESA-INVITe eligibility criteria, vital signs measurement, phlebotomy, urine collection, and study drug dispensing.

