10. ANALYTIC PLAN

We will describe MESA participants screened, enrolled, and completing this ancillary study according to CONSORT guidelines and compare characteristics of participants who do and do not pass through each of these stages. Primary analyses will include participants who complete baseline and 16-week follow-up regardless of adherence. Secondary analyses will include all consented participants using multiple imputation to address data missing from the 16-week follow-up visit.

We will construct linear models for the follow-up value of each outcome variable to determine whether common and rare polymorphisms in six candidate genes modify vitamin D₃ treatment effects: *CYP2R1*, *CYP24A1*, *CYP27B1*, *CYP3A4*, *SULT2A1*, and *VDR*. Independent variables in the model will include treatment group, number of minor alleles at a given locus, the interaction between treatment group and number of minor alleles, the baseline value of the outcome variable, and the following preselected precision variables: age, gender, BMI, season, and the estimated glomerular filtration rate (GFR). Given sample size limitations we will conduct primary genetic analyses among only the white and Black subgroups with potential associations carried to the Chinese and Hispanic groups. Power to detect genetic associations of common variants are shown in Table 1. Secondary genetic analyses are planned to explore all measured and imputed genetic variants with >5% minor allele frequency derived from the Affymetrix 6.0 chip and 1000 Genomes imputation using the regression framework described above.

Table 1. Power for analyses of common variants.

Minor allele frequency	All	White	Black
0.1	0.013	0.001	0.001
0.2	0.141	0.013	0.006
0.3	0.357	0.045	0.021
0.4	0.521	0.083	0.041

We will test whether race/ethnicity, gender, body mass, index, estimated GFR, and serum concentrations of 25(OH)D, bioavailable 25(OH)D, and 24,25(OH)₂D₃ modify the response to vitamin D₃ treatment using analogous regression models to those described above.

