The overall design of the study has not changed. INVITE remains a randomized two-arm, double-blind clinical trial with a 3:1 ratio of assignment to active vitamin D treatment versus placebo. We discussed the possibility of removing the placebo group to create a treatment only study; however, implementing such a change after recruitment of greater than 75% of participants would be difficult to explain to the DSMB, the MESA study sites, and the participants themselves. Moreover, we believe that such a change in design would diminish the impact of manuscripts resulting from this study.

Unlike typical event driven trials, INVITE seeks to identify characteristics that modify the response to treatment. To increase study power to detect such associations, we will start by evaluating only participants who are treated with active vitamin D to assess main effects of genetic polymorphisms and clinical characteristics on the changes in study outcomes. In parallel we will present analytic results from our original approach, in which we analyze all participants and test the interaction of relevant exposures with treatment assignment.

Changes to sample size and study power

Study power for the treatment only analytic approach is considerably greater than that of the original interaction-based analyses. Differences in the effect of vitamin D treatment on study outcomes of change in parathyroid hormone, 1,25-dihydroxyvitamin D, and urine calcium to creatinine ratios according to a modifying genetic polymorphism are presented below. Under the anticipated sample size of 682, the INVITE study will maintain power to detect clinically relevant associations. The INVITE DSMB, which includes a faculty biostatistician, met on September 13, 2018, at which time it reviewed and approved these changes to the analytic plan and power.

Figure2. Minimal detectable associations for genetic polymorphisms under a treatment-only analysis.

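### Relatives may enrol together, but the treatment-only analysis makes no allowance for relatedness, so its standard errors for genotype and race/ethnicity will be modestly too small if they do.

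*Combined protocol and SAP*

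**What the plan says.** **Who may enrol.** Section 4 states that "Up to three MESA cohorts will be approached for study recruitment". The Study Population entry of the Protocol Summary lists MESA Classic first, then MESA Air Family and New Recruit participants, then "Non-MESA Air Family participants". Two of the three sources therefore contain Family participants, and section 4 explains that "MESA Family participants are mainly siblings and parents of MESA Classic participants who were recruited in 2004-2006 for genetics-based studies". The route has working procedures: "MESA Air and MESA Family participants will be recruited either during follow-up phone calls, or during a MESA INVITE-specific recruitment phone call", and section 8.1 adds that "All MESA Family and Air participants will use Exam 6-plus visits for basement measurements".

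**What limits enrolment.** "Inclusion criteria are active participation in MESA at one of the five field centers and willingness to participate in a clinical trial". None of the 11 exclusion criteria concerns relatives. Section 5 randomises individuals 3:1, stratified by site only.

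**How the data are modelled.** Section 10 says "We will construct linear models for the follow-up value of each outcome variable". Its independent variables are treatment, minor-allele count, their interaction, the baseline value of the outcome, age, gender, BMI, season and estimated GFR. Race/ethnicity and the other clinical modifiers use analogous models, and the secondary genome-wide analysis uses the same framework. The revised Analytic Plan (Changes to the analytic plan) then says "we will start by evaluating only participants who are treated with active vitamin D to assess main effects of genetic polymorphisms" and clinical characteristics, with the interaction analysis reported in parallel. Neither text mentions relatedness or a variance estimator.

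**The concern.** First-degree relatives share about half their alleles, usually the same race/ethnicity, and possibly part of the outcome residual. When both the exposure and the residual are positively correlated within families, the usual linear-model standard error counts related participants as more information than they provide. Tests of that exposure then reject too often under the null.

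The 2018 revision made this more relevant. In an interaction model, relatives are randomised separately, so the treatment contrast is not aligned with family membership. In a treatment-only analysis that protection is gone, because the genotype or race/ethnicity slope is estimated directly among treated relatives. Identifying such modifiers is the trial's primary aim (section 2), so any excess of false positives falls on its main output.

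**Working it through.** **No plan figure to reproduce.** Neither document quantifies relatedness. Table 1 gives power for common variants but not the significance level, effect size or standard deviation behind it, so it cannot be reproduced from stated inputs. This point does not dispute it.

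**Inputs from the documents.** Individual 3:1 randomisation (section 5), so a treated participant's co-enrolled relative is also treated with probability about 0.75. Revised sample size 682, of whom 682 × 0.75 ≈ 512 are treated.

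**Assumed inputs, not in the documents.**
- f, the share of enrollees with a co-enrolled first-degree relative: 10% to 40%.
- r, the residual outcome correlation between such relatives after the model covariates: 0.2 to 0.5.
- c, the within-pair correlation of the exposure: 0.5 for an additive genotype, 1.0 for race/ethnicity (taken as fully shared).

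**Treatment-only analysis.** For related pairs,

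variance ratio (true ÷ model) = 1 + f × 0.75 × r × c

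actual two-sided error = 2 × [1 − Φ(z ÷ √ratio)], where z is the nominal critical value.

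| Exposure | f | r | Variance ratio | SE ratio | Actual error at nominal 5% |
|---|---|---|---|---|---|
| Genotype | 0.10 | 0.2 | 1 + 0.10×0.75×0.2×0.5 = 1.0075 | 1.004 | 5.1% |
| Genotype | 0.40 | 0.5 | 1 + 0.40×0.75×0.5×0.5 = 1.075 | 1.037 | 5.9% |
| Race/ethnicity | 0.10 | 0.2 | 1 + 0.10×0.75×0.2×1.0 = 1.015 | 1.007 | 5.2% |
| Race/ethnicity | 0.40 | 0.5 | 1 + 0.40×0.75×0.5×1.0 = 1.15 | 1.072 | 6.8% |

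The documents state no genome-wide threshold. If 5e-8 were used, the genotype ratio of 1.075 would give about 2.9 times the nominal error.

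**Check by simulation.** n = 682, individual 3:1 randomisation, ordinary least squares, 20,000 replicates, residual correlation 0.4:

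| Analysis | 40% in sibling pairs: SE ratio (type I error) | Everyone in a sibling pair: SE ratio (type I error) |
|---|---|---|
| Treatment-only, genotype | 1.03 (0.058) | 1.07 (0.069) |
| Treatment-only, race | 1.06 (0.066) | 1.15 (0.087) |
| Genotype × treatment | 1.00 (0.049) | 1.00 (0.052) |
| Race × treatment | 0.99 (0.048) | 0.99 (0.051) |

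At f = 0.4 and r = 0.4 the formula gives √1.06 = 1.030 for genotype and √1.12 = 1.058 for race, in agreement with the first column. If the family correlation exists only under treatment, the interaction SE ratios rise to at most about 1.02 (genotype) and 1.04 (race), and only when everyone is in a pair.

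**The case against.** A reader might infer that every genetic and race/ethnicity standard error in the plan is too small. That does not hold. The interaction analysis, kept in parallel, is protected by individual randomisation, and its simulated SE ratio is about 1.00.

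Several further points count against a large effect:

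- **Few relatives may have enrolled.** The text says only that up to three cohorts will be approached. Section 12.1 proposes recruiting from the sixth exam. The revised Analytic Plan, at 523 enrolled, names extra visits, a washout option and a fifth site as recruitment measures, but not Family recruitment, although its list is not presented as complete. Returning participants average 70.3 years, so co-enrolled parents are unlikely.
- **Both relatives must be analysed.** The primary analysis also requires both to complete follow-up, which lowers the effective share further.
- **The top of the r range is generous.** The model conditions on each person's own baseline value, and nothing in the documents supports a remaining correlation of 0.5.
- **Genotypes for Family members are not confirmed.** Section 12.1 describes DNA collected in 2000-2002, before Family recruitment, although section 4 says that the Family cohort was recruited for genetics-based studies.
- **Silence is not a decision.** The plan never states that participants are independent, and a list of independent variables would not show a clustered variance estimator.

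These points limit the size and certainty of the problem. They do not remove it: relatives are eligible, the recruitment route is in place, and linear models run as written would by default use standard errors that assume independence.

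**Conclusion.** The concern holds for the treatment-only main-effects analysis, on condition that relatives co-enrol and their residual outcomes are positively correlated. Under the assumed ranges the excess false-positive rate at nominal 5% is at most about 0.9 percentage points for genotype and 1.8 for race/ethnicity. Larger families or stronger correlation would raise these figures; few co-enrolled relatives would bring them close to zero. The documents do not support extending the finding to the interaction analysis, or saying that the standard errors are certain to be wrong. This is a modest weakness, worth correcting because it bears on the analysis now placed first and is cheap to remove.

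**What to change.** In section 10 and in the revised Analytic Plan:

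1. Report how many enrolled, treated and analysed participants have a first-degree relative in the same set.
2. For the treatment-only genetic and clinical models, fit a linear mixed model with a kinship or pedigree random effect, using the MESA family identifiers. For the candidate-gene and clinical models, family-clustered robust standard errors would also serve.
3. Apply the same method to the interaction models as a sensitivity analysis.

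The cost is revised wording, standard software, a little more analysis work and slightly wider standard errors. No extra participants or data collection are needed. If few relatives enrolled, the results will barely change.
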